Biostatistician, (BS). **[name]** will be responsible for conducting semi-annual interim data analyses, generating semi-annual AE safety reports from the electronic study research database and disseminating de-identified information to all members of the DSMC. The interim data analyses will only include safety related results; analyses in regards to study outcome will not be performed. The interim AE safety reports will provide typology, frequency data and outcomes of all reported and documented AEs in the electronic study database. As a member of the DSMC, [name] will also participate in semi-annual DSMC meetings.

Project Manager, (PM). **[name]** will be responsible for the classification of all reported adverse events (AE) and ensuring that all serious adverse events (SAE) are forwarded to the PI and SP in real time and in compliance with MUSC IRB and NINR's reporting requirements. In addition, and in conjunction with the PI, the [name] will be responsible for amending the protocol in accordance with the DSMC recommendations, submitting reportable SAEs to the IRB, and submitting annual Progress Reports to the NIH/NINR through MUSC's OSRP. As part of the DSMC, he will be responsible for: conducting monthly internal quality control audits on all participant records and notifying the PI of any deficiencies; assisting in the generation of ad hoc participant data safety reports as requested; and, the forwarding of reportable SAE to the NIH/NINR Program Official through MUSC's OSRP within 72hrs of IRB review and acknowledgement. [name] will also be responsible for following up on reported AEs to monitor outcomes and provide for the continuity of care for study participants.

SECTION B. Procedures for Safety, Risk and Confidentiality

1) Monitoring Study Safety

From the initial screening of participant by inclusion and exclusion criteria to the informed consent process to the provision of participant study instruction to staff training in Good Clinical Practices (GCP) and regulations pertaining to the Conduct of Human Participant Research to weekly contact with participants to internal quality control audits and protocol fidelity monitoring to the real-time review of AE by the SP and DSMC to the oversight of MUSC's IRB, procedures for monitoring study safety are consistently afforded throughout study. Specific procedures include:

- All participants will be screened for inclusion and exclusion per the protocol
- All participants will be fully informed as to all known risks and the possibility of risk from study participation in the informed consent process. These risks are minimal.
- AEs and changes in medical status will be elicited at every participant visit and contact.
- All participants will be given a 24 hrs. AE reporting phone number to the study nurse and instructed to notify the researchers of any/all suspected or experienced adverse events whether they believe them to be related to the intervention or not.

- The SP will have access to real-time AE study data and will be able to provide immediate recommendations to the PI and PM.
- The PM will track all reported participant AEs through to resolution. Please see Section C. 1 – 4.
- The BS shall generate semi-annual AE reports for the PI and DSMC to review.
- The PM will conduct a quarterly internal quality control audit of the study and all participant records to ensure compliance with MUSC IRB regulations and notify the PI of any deficiencies; the PM will work with the PM to correct any errors.
- The PI and/or designee will observe and evaluate ten (10%) percent of eligibility screening visits, informed consents and study instructions performed by IRB approved study personnel and provide feedback and/or retraining of study personnel if fidelity to both applicable federal regulations and the protocol is not observed.
- All investigators and researchers will maintain active CITI training.
- Investigator performance and compliance will be provided for through MUSC IRB and ORI study oversight.
- All reportable events, including protocol deviations will be forwarded to the NIH/NINR Program Official through MUSC's OSRP within 72hrs of IRB review and acknowledgement.

2) Minimizing Research-Associated Risk

Diligent study safety monitoring will be conducted by the PI and all members of the DSMC throughout the conduct of this study in compliance with the following required elements of MUSC IRB's continuing review process:

1. Tracking and follow-up of participant accrual including withdrawn consents will minimize risk by identifying, disclosing, and mitigating any potentially unknown risk(s) of harm to study participants. These risks are minimal.
2. Timely and appropriate reporting of informed consent process deficiencies, protocol deviations, privacy breaches, conflicts of interest, and/or changes in personnel.
3. Ongoing soliciting, monitoring and appropriate reporting of adverse event activities.
4. Timely and appropriate IRB submission of safety-related documents such as audit reports, sponsor progress reports, ISM reports, and other materials or communications that might impact the safe conduct of this study.
5. Active cooperation with the IRB, ACO, sponsor, and other applicable entities in the event of a random or for-cause internal or external audit.

Institution-Wide Assurances

This protocol will be conducted fully in keeping with the signed MUSC IRB Principal Investigator Statement of Assurance and Department Chair's Statement of Assurance, when submitted to the IRB as a required component of the MUSC IRB Human Research Review Application. An application will be submitted to the MUSC IRB if/when this project is approved and funded by NIH/NINR. Assurances include the following safety-related agreements, signed and dated by the PI.

3) Protecting Confidentiality of Participant Data

Participant Screening and Enrollment. All data from participants screened for the study will be entered into electronic study database. Designated research staff will collect, gather, and enter required data (written informed consent, HIPAA Authorization, medical history and demographics) onto study data forms. Screened patients who do not meet study eligibility will have specific screening data entered into the study database. The collected data will be helpful in examining the patient population and feasibility of enrollment criteria and will include gender, age, race and reason for exclusion. All dates will be shifted and other Personal Health Information (PHI) will be removed from the study database upon study completion. All data obtained from this

study will be used for research purposes only and will comply with Federal HIPAA regulations. Master Screening and Enrollment Logs will be maintained by the PM and will be used to prepare reports on accrual and attrition for the PI and DSMC.

Case Report Forms. All proposed study specific case report forms (source documents) for data collection will be designed by the PM in concert with the PI and BS, and transferred by the PM into electronic Case Report Forms (eCRFs) for use in the study's REDCap database. These study specific eCRFs source documents (study logs for correspondence, contact with provider, compensation and other forms such as pre-eligibility screens) will be coded by the participant's unique study ID# for all data collected including study instruments will be maintained in the participant research record and/or their electronic medical record that will be made accessible to study monitors. Completed instruments that require signature on a paper CRF will be scanned and uploaded into the study database to all for remote electronic safety monitoring as well as maintained on file in accordance with MUSC policies and applicable Federal Regulations for the Conduct of Human Participant Research.

Binders. The PM will prepare and maintain a participant-specific binder for each participant containing all non-eCRFs records. A regulatory file will also be maintained to include the IRB-approved Protocol, original Informed Consent documents, HIPAA forms and other study-related regulatory documents. All paper research records and CRFs will be maintained in a locked file cabinet, stored in a room for research files that is accessible only via a password protected entry system that features security cameras, within the College of Nursing. Access to the research records, study database and PHI's will be restricted to study personnel as approved by the PI and MUSC IRB. As with all studies conducted at MUSC, this study is also eligible for a random audit by MUSC Office of Compliance.

Data Processing. This study will use Research Electronic Data Capture (REDCap) for data capture and management. REDCap is a software toolset and workflow methodology for the electronic collection and management of research and clinical trials data. REDCap provides secure, web-based, flexible applications, including real-time validation rules with automated data type and range checks at the time of data entry. Exports are made available for several statistical packages including SPSS, SAS, SATA, R and Microsoft Excel. The study-specific REDCap electronic database will be designed and developed by the PM in concert with the BS. The provision of REDCap is made available through the South Carolina Clinical & Translational Research (SCTR) Institute at MUSC with NIH Grant awards UL1RR029882 and UL1TR000062.

Data Security. Ensuring data security, compliance with 45 CFR 46 and maintaining the integrity of PHI is a top priority. MUSC has Standard Operating Procedures (SOP) to ensure a high level of data security while coordinating electronic and paper data management activities for clinical research trials. The REDCap study database will be hosted in the Biomedical Informatics secure data center at MUSC, a secure environment for data systems and servers on campus, and includes firewall, redundancy, failover capability, backups and extensive security checks. The secure data center has strict access control; only authorized core personnel may access the facility un-escorted. Only authorized users are allowed to connect to the network, and the security of the network is actively monitored. Power and environmental controls have several layers of backups, from interruptible power supplies to alternate and redundant feeds to the local utility company. The REDCap system administrator contributes to the maintenance of institutional disaster recovery and business continuity plans. Load balancers and a highly fault tolerant SAN infrastructure contribute to high availability.

The REDCap system itself has several additional layers of protection including password protection. Access to the data and its security is managed institutionally by sponsored login IDs through a Shibboleth login with an MUSC issued NetID and features a user account management filter that controls who can access the data and to what degree. All personnel must pass an employment background check before being issued an ID. Password complexity, history and expiration standards are implemented at the institutional level. Access to individual REDCap projects and their data is managed by the owner of the project. All transactions are securely delivered to the application using Secure Sockets Layer (SSL – SHA-1 with RSA Encryption; 2048-

bits). It is then transmitted internally (behind the firewall) to the database server. All transactions are logged at the server layer (httpd logging), application layers (REDCap logs activity to a database table), and the database layer, using both query and binary logging. This feature provides audit trails for all changes, queries, data exports and reports. MUSC Information security policies are available at: <https://mainweb-v.musc.edu/security/policy/>

Data Entry. Only MUSC IRB approved study personnel that are authorized to have access to the REDCap study database will be granted password access. Study personnel using computers that are connected to the Internet will directly enter data into the remotely housed database. As such, no electronic study data will be stored on harddrives and/or any portable electronic devices. Additionally, all personnel with access to the database will have current University of Miami CITI training in the Conduct of Human Subject Protections, and their respective institution's HIPAA and Information Security trainings that are completed annually. Each participant will be assigned a unique study identifier, all PHIs will be masked, and data exports will be limited to the PI, the PM and the BS for generating reports and the conduct of statistical data analysis.

Data Monitoring. Ongoing quality control procedures will be implemented for data collection, storage and processing. The PM will conduct monthly monitoring of the study database and generate a report for the PI to review at team meetings. Standing agenda items for these meetings will include participant recruitment and retention, AE's, protocol deviations, data integrity and overall study conduct. The PM will work to resolve and validate discrepant data. Discrepancies that warrant clarification will be sent to appropriate parties for review and resolution. All data entry and changes made in the study database by authorized study personnel will be automatically logged by REDCap, and provide a transparent visible audit trail for reviewers.

SECTION C.

Procedures for Identifying, Reviewing and Reporting Adverse Events

1) Identifying. Potential minimum risks identified for participants are outlined in the Protection of Human Participants and will also be outlined in the IRB-approved informed consent document. Additional unknown risks may occur and, if so, will be identified through diligent monitoring by the PM and the frontline research team throughout the conduct of this study. During the informed consent process, participants will be advised of the potential minimum risks of participation as identified in the IRB-approved informed consent document and reminded throughout the study that the researchers should be promptly informed about any concerns regarding potential side effects, adverse events, or clinical deterioration. Participants will also be instructed to notify the PI and/or designee of any suspected adverse events immediately if possible. Throughout the course of study enrollment, at each study visit, the researchers will elicit information about experienced AEs and monitor participant progress. The PM will maintain an electronic record of all reported adverse events and notify the PM and SP of all reportable events as they occur. The SP will have real-time access to the study database to review and monitor all SAEs that were reported as related to the intervention. The PM will generate and provide de-identified semi-annual administrative human participant safety reports for the DSMC to review participant progress, accrual and attrition rates. Additionally, the BS will generate semi-annual safety reports for the DSMC to provide for the monitoring of the frequency of all reported side effects and AEs.

2) Reviewing. Adverse events will be assessed and evaluated by the members of the DSMC according to the following MUSC's IRB Adverse Event Reporting Policy

<http://academicdepartments.musc.edu/research/ori/irb/HRPP/HRPP%20Guide%20Section%204.7>:

- *Expected/Anticipated*—Identified in nature, severity, or frequency in the current protocol, informed consent, investigator brochure, or with other current risk information.

- *Unexpected/Unanticipated*—Not identified in nature, severity, or frequency in the current protocol, informed consent, investigator brochure, or with other current risk information.
- *More Prevalent*—Occurs more frequently than anticipated or at a higher prevalence than expected.
- *Serious*—Results in death, is life threatening, requires inpatient hospitalization or prolongs existing hospitalization, results in persistent or significant disability/incapacity, cancer, overdose, or causes a congenital anomaly/birth defect.

The relationship of adverse events to study participation will be determined by the DSMC according to the MUSC IRB Adverse Event Reporting Policy:

- *Unrelated*—There is not a reasonable possibility that the adverse event may have been caused by the drug, device or intervention.
- *Possibly Related*—The adverse event may have been caused by the drug, device, or intervention, however there is insufficient information to determine the likelihood of this possibility.
- *Related*—There is a reasonable possibility that the adverse event may have been caused by the drug, device or intervention.

3) Reporting. All reportable AE, SAE and unanticipated problems experienced by participants will be reported to the NIH/NINR and MUSC IRB in compliance with their Adverse Event Reporting Policy requirements, using the IRB's password protected on-line secure server adverse event reporting system. Within 24 hours after a reportable AE, SAE or unanticipated problem has been reported by the participant, it will be initially graded by the PM, forwarded to the study's SP for review and approval, and then will be submitted by the PI to MUSC IRB. The Institutional Official(s) will review the event and discuss the report with the IRB Chair and the Director of the Office of Research Integrity. After IRB review and acknowledgement, the PI will further review, and the PM will forward a copy of the reportable AE, SAE or unanticipated problem and IRB acknowledgement letter to the NIH/NINR Program Officer through MUSC's OSRP. The activities will be reported to the NIH/NINR within 72hrs. In addition, all cumulative reportable AE, SAE and unanticipated problems included in the ISM reports will be submitted to the NIH/NINR in the PI's Annual Progress Reports.

4) Examples of Potential Reportable Adverse Events: In accordance with MUSC IRB Adverse Event Reporting Policy, an AE is reportable if it meets all of the following criteria: 1) is unexpected 2) is related and/or possibly related, and 3) is serious and/or suggests that the research places participants or others at a greater risk of physical or psychological harm than was previously known or recognized. Additionally, per MUSC's policy all participant deaths, protocol deviations, complaints about the research, and breaches of confidentiality are reportable events. From our previous work among this comorbid population, an example of an AE would be the appearance of edema of the lower extremities that is related to the participant's underlying chronic venous insufficiency. Depending on the severity, the possible steps to be taken include referral to a medical provider, and/or withdrawing the participant from the study and inviting him or her to restart after acute symptoms subside. An example of an SAE would be the death of a participant from acute renal failure, which although would be viewed as unexpected and unrelated to the intervention is nonetheless a reportable serious event. No further steps would be taken except to review, grade and report the event to all applicable agencies. An example of an unanticipated problem would be the participant strains his or her back while taking their temperature of the ulcer "hot spot". The steps in this case would be to withdraw the participant from the study and invite him or her to restart the study after the strain has resolved. These events and problems will be reported in accordance with the IRB and NIH/NINR policy as noted in Section C.3.

SECTION D. Multi-site Monitoring and Compliance

This is not a multi-site study.

SECTION E. Assessment of External Factors

The PI will conduct a semi annual assessment of external factors through a review of literature related to new developments in the areas of diabetic foot ulcer and venous leg ulcer prevention, and other approaches that may have an impact on the safety of participants or on the ethics of the study. To determine whether any changes are necessitated to the study protocol, the DSMC will review any identified literature or product safety data that may pose as a potential impact to the risk benefit ratio study and/or safety of study participants.

SECTION F. Interim Analysis

Based upon our prior extensive research in this field among this same population and the minimal risk associated with the intervention, there is no stopping rule for this study. Accordingly, interim futility analysis will not be performed. However, the BS and PM will generate semi-annual qualitative interim analysis reports on a) adverse events; and b) data obtained during phone call and returned end-of-study surveys to understand issues related to the uptake, usability, and adoption of the cooling protocol among this population. We will evaluate the screening and enrollment procedures, barriers to participation and retention, including, safety, adherence, acceptability, technology problems (thermometer malfunction) encountered if any, and user feedback from the participants. The information gained from this structured process will inform the design for an implementation/dissemination study aimed to facilitate the use a leg and foot ulcer prediction/prevention standard of care.

F. REFERENCES/LITERATURE CITATIONS

2. [name] M, Schoess J, Armstrong DG. Coming events cast their shadows before: Detecting inflammation in the acute diabetic foot and the foot in remission. *Diabetes/metabolism research and reviews*. 2012;28 Suppl 1:15--20. doi: 10.1002/dmrr.2231.
3. Sayre EK, [name] TJ, Neal D. Sudden increase in skin temperature predicts venous ulcers: A case study. *Journal of vascular nursing : official publication of the Society for Peripheral Vascular Nursing*. 2007;25(3):46--50. doi: 10.1016/j.jvn.2007.06.002.

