prophylactically cooling a focal or localized area of affected skin reduces the risk of skin changes and ulceration by reducing microcirculatory blood flow, vessel permeability and tissue metabolism ⁵⁵. **Preliminary work.** The preliminary findings from our cryotherapy R21 suggested a signal of efficacy in reducing tissue metabolism (blood flow), pain reduction and ulcer prevention ¹⁹. Cooling the skin significantly reduced blood flow on average by 6 perfusion units (PU), from 15 to 9 PU (normal is 3 – 5 PU) after four weeks of cooling ¹⁸. We also found that vasoconstriction and reduced blood flow can persist for greater than one hour after removal of cryotherapy, even in the presence of skin rewarming at room air ⁵⁶. We developed this proposed study's protocol based on principles of heat transfer, microcirculatory thermoregulation, studies of cryotherapy and healthy skin, and pathophysiologic mechanisms of venous disorders, supplemented with consultation with [name], and additional preliminary work conducted post R21. In regards to pain, cryotherapy offers an analgesic effect that can be realized within 3 minutes by locally deactivating pain receptors, which are located in the subcutaneous tissue ^{57,58}. These findings led to the currently funded R01 to test the efficacy of a sequenced cooling regimen over a 9-month period for patients with venous disease, damaged skin and/or a history of healed venous ulcers. The ongoing study is evaluating efficacy on pain, ulcer occurrence and quality of life (in year 4). While we are in the last year of the study and will analyze data to determine outcomes on ulcer prevention, first month data (§Figure 1) suggest that an initial acute daily cooling regimen, compared to a placebo, demonstrated a clinically, but no statistically significant difference in skin temperatures measured daily (cryotherapy cuff treatment + leg elevation versus placebo cuff + leg elevation.) There was a non-significant trend towards lower skin temperatures in both groups. These findings suggest that an acute cooling period is unnecessary and that a reduced frequency (three times weekly for 30 minutes based on our preliminary data) could be adequate as a maintenance dose to keep the skin temperature "in check". These findings are further supported by [name] inflammation proof of concept work in diabetes ⁵⁹ and [name] post-operative cryotherapy research ⁶⁰.

[figure not shown]

Figure 1.

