Self-management with cooling pack – Participants in both groups will apply the pack (cooling or placebo) at a consistent time each day (e.g. 7 PM) to the affected leg or foot skin “hot spot”, both prophylactically (maintenance) and preventatively (bolus dosing) (§Table 2). The rationale for using cooling packs compared to cuffs or wraps is based on exit interview comments from participant experiences in our ongoing cryotherapy R01 in which a lower leg cooling cuff (regional cooling of the lower leg) was used. Some of the user comments include: “I felt cold all over when using the cuff”, “why do we need to cool so much skin when it’s just that one area that has the problem?”, “that cuff was too heavy and weighed down my leg”, and “the nurse worked so hard to make it fit but it didn’t feel right on my leg”. In response, the proposed study will use readily available small packs, applied only locally (versus regionally) to the “hot spot” on the leg or foot (§Table 3 for refinements to study protocol). The topical cooling pack (Therapy Pack, Elastogel, Southwest Technologies, Kansas City, MO) to be used in the cooling treatment group is a flexible glycerin-based sheet hydrogel that does not freeze to a solid state and is available in various sizes. We have conducted extensive safety testing of the material prior to our previously conducted R21 and have had no adverse events (e.g., skin injury) reported during the R21 and the ongoing cryotherapy R01. The placebo pack has a cotton lining (manufactured by same company and used in our ongoing R01). Both packs have the same feel and look and are covered with a protective polyethylene covering that can be laundered. Both packs will be stored in the freezer (will give subjects freezer thermometers to make sure freezer temperature is maintained at 0°F) and will be applied to the affected site only. Once removed from the freezer, the placebo pack warms to room temperature within 2 minutes. The packs will be anchored with a tubular retainer that is an expandable elastic latex-free net. Participants will record the date and times they apply the packs to the skin (three times each week for maintenance and 5 consecutive days for bolus dosing) on the “back up” log.

TABLE 3: SELF MONITORING & MANAGING SIX- MONTH DOSING REGIMEN FOR BOTH GROUPS		
Monitoring	Daily each morning	Temperature date and time stamped in thermometer
Management dosing	Maintenance	Bolus

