
E. PROTECTION OF HUMAN SUBJECTS

Participants, 18 years-of-age and older, will be included in the study. The participants must be able to communicate in English. The study will include both genders and to ensure diversity, participants from various racial backgrounds representative of the area (~30% black/African-American, ~70% white, ~1% Hispanic/ /other) will be invited to participate. There are minimal risks for injury related to **MUSTCOOL**. There have been no reports of skin injury associated with the cryotherapy (cooling) intervention used in our ongoing R01, which is the same intervention that will be used in this proposed study to reduce inflammation (skin temperature). We have taken more precautions regarding avoidance of frostbite or other cooling related injuries (e.g. skin irritation) by reducing the area of the skin to be cooled, from regional (cuff applied to entire lower leg) to only a small, localized area of the foot or lower leg. Participants will be instructed to report symptoms such as tingling, prickling, and other sensations if noted during cooling. The informed consent and Health Insurance Portability and Accountability forms assure confidentiality of all information obtained during the study. Participants have the right to withdraw from the study at any time without any effect on the care they will receive in the future. Informed consent, approved by the Institutional Review Committee, will be obtained by study personnel and signed by the participant indicating willingness to participate in the study.

E.1. RISKS TO THE SUBJECTS

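### The no-stopping-rule rationale cites the same population, but the stated no-harm experience is from venous disease; no diabetic foot ulcer (DFU) adverse-event result is given and safety tables are not split by ulcer type

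*Combined protocol and SAP*

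**What the plan says.** **Waiver.** DSMP Section F (Interim Analysis) invokes earlier research and then reads "among this same population and the minimal risk associated with the intervention, there is no stopping rule for this study". Its two grounds are the population and minimal risk.

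**No-harm experience.** D.9 (Self-management with cooling pack) says the investigators "have had no adverse events (e.g., skin injury) reported during the R21 and the ongoing cryotherapy R01". The Safety paragraph under Impact, section E and E.1.c make similar statements; section E and E.1.c point to the ongoing study.

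**Who and what that covered.** Section 1.1 (Preliminary Studies) describes the R01 as testing "a sequenced cooling regimen over a 9-month period for patients with venous disease, damaged skin and/or a history of healed venous ulcers". D.9 says that in it "a lower leg cooling cuff (regional cooling of the lower leg) was used". The blood-flow report cited beside the R21 (reference 18) concerns a gel wrap on skin with chronic venous disorders. Section E says of the R01 cooling, "which is the same intervention that will be used in this proposed study".

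**This trial.** E.1.a plans 90 venous and 90 DFU participants. D.7 stratifies randomisation by ulcer type.

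**Safety analysis.** The Aim 1 analysis plan compares adverse-event proportions for cooling against placebo. DSMP Section A has the biostatistician report the type, frequency and outcome of events twice a year. Neither mentions ulcer type.

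**The concern.** Citing prior research in the same population tells the reader that the harm profile is already known for the people being enrolled. For DFU participants, the plan reports nothing from which that could be judged. DSMP Section C also classes events as unexpected or more prevalent relative to known risk, and for DFU there is no stated reference rate.

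One listed safeguard depends on sensation. Section E says: "Participants will be instructed to report symptoms such as tingling, prickling, and other sensations if noted during cooling". Yet section B includes neuropathy in the target population, and the outcome section gives the neuropathic pain questionnaire to the DFU participants.

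If cooling harmed only DFU participants, pooling would put those events over a denominator twice the size of the group at risk. The report would not show that they clustered in one stratum.

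**Working it through.** The plan gives no figure to reproduce here. The first part of the check traces text; the second sizes the dilution.

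**Tracing the evidence**

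| Source of experience | Population stated | Device stated | DFU adverse-event result |
|---|---|---|---|
| R01 (1.1, D.9, reference 19) | Venous disease | Lower-leg cuff | None |
| R21-era report (1.1, reference 18) | Chronic venous disorders | Gel wrap | None |
| Table 1, earlier protocol column | Any VLU or DFU patient | Cuff on leg or foot | None |
| Diabetic-foot cooling references (55, 59) | Diabetic foot | Foot cooling; cold immersion | None carried into the plan |

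The R21 population is inferred from the report cited with it. The no-adverse-event statements carry no denominators or patient-time, even for venous patients.

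**Tracing the split.** The line repeating analyses within VLU and DFU closes the recurrence paragraph of the Aim 1 plan. The adverse-event sentence comes two paragraphs later and names arm only. DSMP Sections A, C and F describe the semi-annual reports without a breakdown by ulcer type.

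**Number of DFU participants cooled.** Equal allocation is assumed.
- E.1.a: 90 / 2 = 45.
- D.8's N = 240, assuming half are DFU: 120 / 2 = 60.

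**Dilution.** The 5% rate is an assumption, not a figure from the documents. With a 5% rate in DFU and 0% in VLU, the pooled cooling-arm rate is (45 × 5% + 45 × 0%) / 90 = 2.5%.

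**What zero events would show.** The one-sided 95% upper bound is 1 − 0.05^(1/n).
- n = 45: 6.4%
- n = 60: 4.9%
- n = 90 (pooled): 3.3%
- n = 120 (pooled, N = 240): 2.5%

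**Would a DFU-only test help?** Assume 10% in cooled DFU participants and 1% in everyone else. The pooled cooling rate is (10% + 1%) / 2 = 5.5%. Two-sided 5% normal-approximation power is Φ[(d − 1.96·√(2p̄(1−p̄)/n)) / √((p₁(1−p₁)+p₂(1−p₂))/n)].
- Pooled, 5.5% v 1%, n = 90 per arm: Φ[(0.045 − 1.96 × 0.0264) / 0.0262] ≈ 40%.
- DFU only, 10% v 1%, n = 45 per arm: Φ[(0.090 − 1.96 × 0.0481) / 0.0471] ≈ 46%.

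The counts are sparse, so these are rough. Neither test is well powered, and the value of the split is descriptive.

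**The case against.** The strongest defence is that the safeguards are real.
- DSMP Section A sets up a committee that meets twice a year and may recommend termination.
- Section B gives the safety physician real-time adverse-event data.
- Skin is assessed at each visit, and infrared images are taken at baseline and months 1, 3 and 6.
- Hypersensitivity to cold and conditions impairing skin blood flow are exclusions.
- The Safety paragraph acknowledges that cooling might worsen neuropathic symptoms.

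Having no formal stopping rule in a study classed as minimum risk, with such a committee, is a defensible choice. All of this stands.

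A reader might infer three stronger things that the documents do not support.

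1. *That the waiver rests on an identical intervention.* It does not. That phrase is in section E, and the next sentences there disclose the move from a regional cuff to a small local area. D.9 also reports safety testing of the pack material.
2. *That DFU has no safety base at all.* Table 1 mentions DFU patients and foot use, and two diabetic-foot cooling references are cited. The supportable statement is that no DFU adverse-event result is quoted.
3. *That DFU participants have no safety review.* Pooled review exists. Part of the committee section was also unavailable to this review, so the absence of a split is claimed only for the text seen.

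It is also fair that pooling changes a percentage and not the number or type of events reported, and that 5% is only an illustration.

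**Conclusion.** The point holds in a limited form. The stated no-adverse-event experience is traceable to venous-disease studies with a different device format. It does not support a same-population rationale for the DFU half of the sample, and no ulcer-type split is specified in the safety reports or the final adverse-event comparison.

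The practical effect is up to a twofold dilution of a DFU-only harm rate, and a zero-event bound that looks about half as wide as it is for DFU: 3.3% pooled against 6.4%, or 2.5% against 4.9% under N = 240. These figures assume equal allocation, DFU as half the sample, and, for the 2.5% pooled rate, an assumed 5% DFU rate with none in VLU.

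The primary efficacy analysis is unaffected. The absence of a stopping rule is not itself shown to be wrong. This is a cheap improvement, below must-fix.

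**What to change.** 1. In the adverse-event sentence of the Aim 1 analysis plan and in the biostatistician's duties in DSMP Section A, require every semi-annual and final safety report to tabulate adverse events by ulcer type within coded arm. Give counts and denominators, and show skin and cold-related events as their own category. Present the split descriptively.
2. In the Safety paragraph under Impact, in section E and in DSMP Section F, state that the no-adverse-event experience comes from venous-disease studies with a different device format. If DFU adverse-event data exist, quote them with denominators.
3. Reconcile section E's reliance on reported sensations with section B's inclusion of neuropathy.

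The cost is one extra split on the existing randomisation stratum and a few text edits. Coded arm labels protect masking. The downside is small cells, in which chance imbalances can be over-read. No stopping rule, dose or clinical rule is proposed.
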